***Objective 4: Measure incidence of health outcomes related to influenza***

- Incidence of laboratory-confirmed influenza-associated respiratory hospitalizations will be calculated by dividing the number of respiratory hospitalizations associated with a positive influenza laboratory test observed during each study season by the person-time of the cohort at risk during the corresponding season.
  - This will be calculated for the following risk groups: age group, high-risk conditions, vaccinated for influenza, unvaccinated, race/ethnicity, socio-economic status, etc.
  - Incidence will be compared between risk groups using rate differences or relative rates

- Incidence of ICU admission, mechanical ventilation, and in-hospital death associated with influenza will be similarly calculated, with the respective numerators restricted to those laboratory-confirmed influenza-associated respiratory hospitalizations with the relevant outcomes identified.
  - This will be calculated for the following risk groups where sample size permits: age group, high-risk conditions, vaccinated for influenza, unvaccinated, race/ethnicity, socio-economic status, etc.
  - Incidence will be compared between risk groups using rate differences or relative rates
- Incidence of laboratory-confirmed influenza-associated acute respiratory illness (ARI)-associated outpatient visits will be calculated by dividing the number of ARI visits with a laboratory test positive for influenza observed during each study season by the person-time of the cohort at risk during the corresponding season.
  - This will be calculated for the following risk groups where sample size permits: age group, high-risk conditions, vaccinated for influenza, unvaccinated, race/ethnicity, socio-economic status, etc.
  - Incidence will be compared between risk groups using rate differences or relative rates

As multiple events are possible during a season, incidence estimates throughout this objective may be calculated in two ways: 1) counting only the first occurrence, and 2) counting the cumulative number across the season.

***Objective 5: Assessment of vaccine effectiveness***

- We will estimate the effect of influenza vaccination on risk of lab-confirmed influenza-associated respiratory hospitalization by age group, influenza type/subtype, and high-risk conditions
  - The risk of influenza-associated respiratory hospitalization among cohort members who were or were not vaccinated with the current season influenza will be compared using appropriate methods for longitudinal data with time varying exposure, including Poisson regression or proportional hazards modeling.
  - VE will be estimated as  $(1 - \text{adjusted relative risk}) \times 100$ .
  - We will assess and adjust for confounders as appropriate. These may include characteristics such as age, sex, site, race/ethnicity, high-risk health conditions, prior healthcare utilization, time of event during the influenza season, etc.
  - Data collected for this study are intended to be pooled across sites. VE will first be estimated for each site and heterogeneity in estimated VE across sites examined.
- We will estimate the effect of influenza vaccination on risk of lab-confirmed influenza-associated ARI outpatient visit among children (adults only if influenza testing allows for this) by age group, influenza type/subtype, and high-risk conditions
  - The risk of influenza-associated outpatient visits among cohort members who were or were not vaccinated with the current season influenza will be compared using appropriate methods for longitudinal data with time varying exposure, including Poisson regression or proportional hazards modeling.
  - VE will be estimated as  $(1 - \text{adjusted relative risk}) \times 100$ .

- We will assess and adjust for confounders as appropriate. This may include characteristics such as age group, sex, site, race/ethnicity, high-risk health conditions, prior healthcare utilization, time of event during the influenza season, etc.
- Data collected for this study are intended to be pooled across sites. VE will first be estimated for each site and heterogeneity in estimated VE across sites examined.
- VE analyses against influenza-associated respiratory hospitalizations will also be conducted using a test-negative case-control design
  - This analysis will be conducted among individuals who were hospitalized for acute respiratory illness during the influenza season and who were tested for influenza.
  - Cases will be defined as hospitalized individuals who tested positive for influenza.
  - Controls will be defined as hospitalized individuals who tested negative for influenza.
  - Influenza vaccination status will be determined for all cases and controls and the odds of vaccination will be compared using logistic regression.
  - VE will be estimated as  $(1 - \text{adjusted odds ratio}) \times 100$ .
  - We will assess and adjust for confounders as appropriate. This may include characteristics such as age group, sex, site, race/ethnicity, high-risk health conditions, prior healthcare utilization, time of event during the influenza season, etc.
  - Data collected for this study are intended to be pooled across sites. VE will first be estimated for each site and heterogeneity in estimated VE across sites will be examined.

Beyond the primary objectives listed here, additional analyses may be pursued and will be considered by the joint steering committee.

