## **3.2 Rationale and Justification**

Each year CDC communicates with the public about the burden of influenza and the importance of influenza vaccination and other prevention and control measures. People get vaccinated for influenza in part because they perceive the risk of influenza to the health of themselves and their family to be high and they perceive that the influenza vaccine is effective. Part of CDC’s mission is, then, to empower people by using information and data to protect themselves and their family from influenza.

This mission drives the need to measure the incidence of severe health outcomes related to influenza in a variety of groups, including among pediatric and adult age groups, and by high-risk conditions. Furthermore, it is imperative to understand the effectiveness of influenza vaccination against rare, but severe, complications of influenza in the general population and

also among people with underlying medical conditions. These data are essential to supporting the communication messages that CDC and other public health entities rely on to keep people safe from influenza each year.

To effectively estimate the full burden of severe influenza and address these needs, annual retrospective cohorts of individuals will be constructed from a network of large health systems. Within each cohort, individuals can be linked with their vaccination records and their clinical data can be queried to estimate the incidence of outcomes of interest, including influenza-related hospitalizations and outpatient visits. Building each cohort from clinically available data within health systems that integrate, or link, medical records across an individual's medical encounters will enable the analysis to be stratified by underlying medical conditions. Furthermore, joining multiple health systems together will provide the statistical power to investigate less common underlying conditions or clinical outcomes, like ICU admission.

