### 4.1 Primary Objectives

1. Assess the validity and biases associated with defining the source population based on care-seeking.
  - Compare characteristics of the different cohorts, as defined above, assessing differences in the demographics, the frequency of underlying high-risk conditions, and the frequency of respiratory hospitalizations during influenza season.
2. Assess internal and external validity of influenza vaccination data for current and prior seasons.
  - Internal validity:
    - Assess the accuracy of the derived vaccine status variable in relation to a manual review of records on a subset of the cohort.
    - Describe the contributions to the overall conclusion about vaccination status by various sources from which vaccination data were obtained.
    - Describe the consistency of vaccination data that are available by data source, including date of vaccination, vaccine type, vaccine route, vaccine

lot number, setting in which vaccine was administered, number of doses of vaccine (children <9 years).

- Describe completeness of vaccination data (e.g. date of vaccination, type of vaccine, lot number) by data source for the current season and prior seasons.

- External validity:

- Compare vaccine coverage and data completeness to values reported from other studies with active enrollment / prospective data collection.

3. Assess biases associated with clinical testing for influenza and other respiratory viruses and whether they differ in the inpatient versus outpatient setting:

- Assess the accuracy of the extracted test dates, types, and results in relation to a manual review of records on a subset of the cohort.
- Estimate proportion of cohort enrollees tested for influenza and other respiratory viruses during the influenza season.
- Describe types of influenza and other respiratory virus tests performed on cohort enrollees by pediatric and adult age groups and how test types vary by setting.
- Estimate the proportion of respiratory hospitalizations tested for influenza during the influenza season and factors associated with influenza testing in the inpatient setting including age, high-risk conditions, current season influenza vaccination status, ICU stay, timing of encounter within season, diagnoses codes.

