**5.5 Outcomes of Interest**

- Respiratory illness-associated hospitalizations with laboratory-confirmed influenza
  - Respiratory hospitalizations will be defined using ICD-9 and ICD-10 discharge diagnoses codes as listed in Appendix D.
  - Data on all respiratory hospitalizations will be collected for the entirety of the surveillance period (influenza season).
  - The respiratory hospitalizations will be linked with data on influenza testing to determine if the hospitalization was associated with laboratory-confirmed influenza.
    - Laboratory-confirmed influenza associated respiratory hospitalization will be defined by a positive influenza test within 14 days prior to hospitalization or no more than 3 days after hospital admission.

- Hospitalization will be defined as admission to an inpatient ward or an observation unit. Time spent only in the emergency department will not count as a hospitalization.
- Re-admissions that occur within 30 days of the index hospitalization will be counted as part of the index hospitalization. Readmissions that occur >30 days after the index hospitalization will be considered new hospitalization events.
- ICU admission among persons hospitalized with laboratory-confirmed influenza-associated respiratory hospitalization
- Invasive mechanical ventilation among persons hospitalized with laboratory-confirmed influenza-associated respiratory hospitalization
- In-hospital death among persons hospitalized with laboratory-confirmed influenza-associated respiratory hospitalization
- Acute respiratory illness-associated outpatient visits with laboratory-confirmed influenza
  - Acute respiratory illness-associated outpatient visit will be defined using the ICD-9 and ICD-10 discharge codes listed in Appendix D.
  - Data on all acute respiratory illness-associated outpatient visits will be collected for the entirety of the surveillance period (influenza season).
  - The acute respiratory illness outpatient visit will be linked with data on influenza testing to determine if the visit was associated with a positive influenza laboratory test.

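### Outpatient vaccine effectiveness is estimated by the cohort method alone, so testing differences by vaccination status that survive adjustment bias it; a test-negative analysis of outpatient visits would give a check

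*Protocol*

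**What the plan says.** **Outcome.** Under Section 5.5, an outpatient ARI visit is "linked with data on influenza testing to determine if the visit was associated with a positive influenza laboratory test". No separate rule is given for visits without a test, so an untested visit cannot become a case.

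**Outpatient VE.** Section 6.1, Objective 5, compares vaccinated and unvaccinated cohort members by Poisson or proportional hazards regression and takes VE as one minus the adjusted relative risk. The analysis is for children; adults are added only if outpatient testing is sufficient. The candidate covariates are optional and include age group, site, high-risk conditions, prior utilization and timing in the season. Neither receipt of a test nor the probability of testing is among them.

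**Test-negative design.** It is specified for one outcome: "VE analyses against influenza-associated respiratory hospitalizations will also be conducted using a test-negative case-control design". Its population is tested inpatients.

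**Incidence (Objective 4).** The hospitalization rate comes from "dividing the number of respiratory hospitalizations associated with a positive influenza laboratory test observed during each study season by the person-time of the cohort". The ICU, ventilation and death rates follow, "with the respective numerators restricted to those laboratory-confirmed influenza-associated respiratory hospitalizations with the relevant outcomes identified". The outpatient rate comes from "dividing the number of ARI visits with a laboratory test positive for influenza observed during each study season by the person-time of the cohort". For groups that include high-risk conditions and vaccination status, "Incidence will be compared between risk groups using rate differences or relative rates".

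**Testing (Objective 3).** Section 4.1 plans to study "factors associated with influenza testing in the inpatient setting including age, high-risk conditions, current season influenza vaccination status" and further items, and its next bullet does the same for outpatient ARI visits. Section 6.1 models receipt of a test in both settings. Section 1.4 names bias from clinician-driven testing as something to evaluate, and says in general terms that later objectives will build on the earlier ones. No step carries the Objective 3 result into an Objective 4 or 5 estimator.

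**The concern.** The protocol treats clinician-driven testing as a source of bias and plans to measure it against vaccination status, which is the exposure in the VE analysis. Yet outpatient VE, where testing is uncertain enough that the adult analysis is conditional on it, has only the estimator that is open to this bias. Hospitalization VE shares the weakness in its cohort form, but its test-negative companion provides a check.

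At stake is the outpatient VE estimate under a primary objective. A difference in testing habits could be read as a stronger or weaker vaccine, and the plan has no second outpatient estimate to set against it.

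**Working it through.** The protocol states no figure for this bias, so there is nothing to reproduce. The check is algebra with assumed inputs.

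**Inputs**
- Cohort estimator and outcome definition: Sections 5.5 and 6.1, Objective 5.
- True VE of 40%: assumption, for illustration.
- Testing probabilities among influenza illnesses, t_v (vaccinated) and t_u (unvaccinated), after covariate adjustment: assumption. The protocol gives none. Section 7.4 says only that sites may differ in how much they test.
- Tests taken as perfectly sensitive and specific: assumption.

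**Step 1: cohort estimator.** Let λ be the risk of an influenza ARI visit in the unvaccinated.
- Observed risk, unvaccinated = λ × t_u
- Observed risk, vaccinated = λ × (1 − VE) × t_v
- Observed VE = 1 − (1 − VE) × (t_v / t_u)

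With 1 − VE = 0.6:

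| Assumed t_v / t_u | Calculation | Observed VE |
|---|---|---|
| 0.8 | 1 − 0.6 × 0.8 | 52% |
| 0.9 | 1 − 0.6 × 0.9 | 46% |
| 1.0 | 1 − 0.6 × 1.0 | 40% |
| 1.1 | 1 − 0.6 × 1.1 | 34% |
| 1.25 | 1 − 0.6 × 1.25 | 25% |

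For a vaccine with no effect, 0.8 gives 1 − 0.8 = 20%, and 1.25 gives 1 − 1.25 = −25%.

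**Step 2: test-negative estimator on the same data.** Let μ be the risk of a non-influenza ARI visit, equal in both groups, and let testing depend on vaccination but not on the virus present. Take t_v = 0.4 and t_u = 0.5, a ratio of 0.8.
- Vaccinated: cases 0.6λ × 0.4 = 0.24λ; controls 0.4μ; odds 0.6 λ/μ
- Unvaccinated: cases 0.5λ; controls 0.5μ; odds λ/μ
- Odds ratio 0.6, so VE = 40%

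The cohort estimate from the same figures is 1 − 0.24/0.50 = 52%. The testing probability enters cases and controls alike and cancels. Reversing the probabilities (0.5 and 0.4) gives a cohort VE of 25%, and again 40% from the test-negative analysis.

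**Step 3: Objective 4.** By the same algebra, observed rate ratio = true rate ratio × ratio of P(tested | influenza illness). No adjustment is stated for these comparisons. Two groups with equal true rates, one tested 1.5 times as often when ill with influenza, would show a rate ratio of 1.5. Whether any such ratio applies here cannot be learned from the protocol.

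**The case against.** **The protocol is staged.** Testing bias is a primary objective in its own right, the later objectives are meant to build on it, and Section 6.1 leaves room for additional analyses. Choosing a correction once Objective 3 has reported is reasonable. This stands in part. But Section 6.1 itself names the estimators and limits the test-negative design to hospitalizations, and the general statement of intent contains no method.

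**Covariates absorb some of it.** This stands. Site, age, high-risk conditions, prior utilization and timing, if used, remove the part of the testing difference that they explain. Only the residual difference by vaccination status biases VE.

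**The bias would not go unseen.** This also stands. A reader might infer that the plan could not detect differential testing. In fact the outpatient regression in Objective 3 would show it, and making adult VE conditional on adequate testing is a safeguard. What is missing is an outpatient estimate less exposed to it.

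**Objective 4 reports what it says.** Its outcomes are labelled laboratory-confirmed, so the crude rates are valid as rates of confirmed events. The stated motive, "To effectively estimate the full burden of severe influenza", is rationale rather than a definition of the quantity estimated.

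**A larger effect on Objective 4 is tempting but unsupported.** A reader might suppose that 60% of high-risk and 30–40% of other admissions are tested, and infer that the rate ratio is inflated 0.6/0.4 = 1.5 to 0.6/0.3 = 2 times. Those shares are not in the protocol. They are also the wrong probability: the factor is the ratio of testing among influenza illnesses. The two ratios agree only if testing is aimed at influenza to the same degree in both groups, for instance if it is unrelated to having influenza. Clinicians may well test on suspicion.

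**Weighted rates as the main comparison are also tempting.** Weighting each positive by the inverse of its testing probability assumes that untested visits would have been positive as often as tested ones within strata. The outpatient codes in Appendix D include headache, malaise, otitis media and screening encounters, where that may fail and the weights could overstate influenza.

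**Conclusion.** The point holds for outpatient VE. The single estimator specified is biased by any testing difference between vaccinated and unvaccinated influenza illnesses that remains after adjustment, and the protocol reserves the design that conditions on testing for inpatients. With a true VE of 40%, residual ratios of 0.8 and 1.25 shift the estimate to 52% and 25%. These are illustrations: they rest on assumed ratios and perfect tests, and the protocol fixes neither the size nor the direction.

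For Objective 4 the same mechanism exists, but the protocol supports no inflation figure and gives no ground for replacing the crude confirmed rates.

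**What to change.** **Outpatient VE.** In Section 6.1, Objective 5, extend the test-negative analysis to outpatient ARI visits tested for influenza: test-positive cases, test-negative controls, logistic regression with the inpatient covariates including timing in the season. Report it beside the cohort estimate, each with its assumptions.

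**Incidence.** In Objective 4, keep the crude laboratory-confirmed rates as primary. Add testing-adjusted rates from the Objective 3 model, with diagnoses among the predictors, as a sensitivity analysis only, and state the equal-positivity assumption. Any statement about inflated rate ratios should be made conditional on the testing ratio among influenza illnesses.

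**Cost.** Analysis code only. Section 5.4 already extracts all test results with encounter type and specimen date, and Section 5.6 captures ARI encounters separately from testing, so untested visits can be identified. The price is fewer records in the test-negative analysis, and reliance on testing not depending on the virus present given the covariates.

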## **6.2 Sample Size**

Table 1 presents sample size requirements for the primary objective of VE against severe outcomes. Existing data from hospital-based surveillance was used to estimate the reported incidence of laboratory-confirmed hospitalizations, ICU admissions, and deaths. Data from the Behavioral Risk Factor Surveillance System (BRFSS) and National Health Interview Survey (NHIS) was used to estimate vaccine coverage.

For adults, we assumed vaccine coverage of 30% in adults aged 18-49 years, 42% in adults aged 50-64 years, and 65% in adults 65 years and older. We assumed a population made up of 33% of adults in each of the three age groups.

For children, we assumed vaccine coverage of 70% in children aged 6 months to 4 years and 50% in children aged 5 to 17 years. We assumed a population made up of 50% of children in each of the two age groups.

Table 1 Sample Size Estimations

|                              | Minimum Detectable VE | Person-years needed |             |
|------------------------------|-----------------------|---------------------|-------------|
|                              |                       | Adults              | Pediatrics  |
| VE against hospitalization   | 40%                   |                     | 398,319     |
|                              | 35%                   | 197,593             | 569,374     |
|                              | 30%                   | 292,719             | 842,278     |
|                              | 25%                   | 456,014             | 1.3 million |
|                              | 20%                   | 766,799             |             |
| VE against ICU admission     | 40%                   |                     | 1.01 m      |
|                              | 35%                   | 1.2 million         | 1.4 m       |
|                              | 30%                   | 1.8 m               | 1.9 m       |
|                              | 25%                   | 2.8 m               | 2.8 m       |
|                              | 20%                   | 4.8 m               |             |
| VE against in-hospital death | 40%                   |                     | 28.1 m      |
|                              | 35%                   | 5.4 m               | 39.4 m      |
|                              | 30%                   | 7.9 m               | 52.8 m      |
|                              | 25%                   | 12.4 m              | 73.8 m      |
|                              | 20%                   | 20.8 m              |             |

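### Table 1's pediatric rows do not agree with each other: person-years for ICU admission and death do not scale with those for hospitalization, and the protocol does not show which row is wrong

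*Protocol*

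**What the plan says.** Section 6.2 opens with "Table 1 presents sample size requirements for the primary objective of VE against severe outcomes". On event rates it says "Existing data from hospital-based surveillance was used to estimate the reported incidence of laboratory-confirmed hospitalizations, ICU admissions, and deaths", but prints no rates. The pediatric coverage assumption reads "we assumed vaccine coverage of 70% in children aged 6 months to 4 years and 50% in children aged 5 to 17 years"; the age mix is given as "We assumed a population made up of 50% of children in each of the two age groups". Nothing suggests that these assumptions differ by outcome. The adult coverage assumption reads "we assumed vaccine coverage of 30% in adults aged 18-49 years, 42% in adults aged 50-64 years, and 65% in adults 65 years and older", with a third of the population in each age group.

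Pediatric person-years printed in Table 1:

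| VE | Hospitalization | ICU | In-hospital death |
|---|---|---|---|
| 40% | 398,319 | 1.01 m | 28.1 m |
| 35% | 569,374 | 1.4 m | 39.4 m |
| 30% | 842,278 | 1.9 m | 52.8 m |
| 25% | 1.3 million | 2.8 m | 73.8 m |

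Section 6.2 states no alpha, power or formula. In section 4.1, Objective 5 lists hospitalization, ICU admission and outpatient influenza as the VE outcomes. It does not list in-hospital death.

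**The concern.** With coverage and target VE fixed, the person-years needed for a rare event are inversely proportional to the event rate. Going from hospitalization to ICU admission or death should therefore multiply every entry in the column by about the same constant. The adult column behaves this way and the pediatric column does not. Table 1 is the protocol's only size justification for VE, and ICU admission at all ages is a named Objective 5 outcome. A reader who uses the pediatric ICU figures cannot tell which VE the network could detect.

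**Working it through.** **Inputs.** Table 1 as printed. Pediatric coverage is 70% and 50% in equal halves, so 60% on average. VE is one minus the relative risk, following section 6.1 ("The risk of influenza-associated respiratory hospitalization among cohort members who were or were not vaccinated with the current season influenza will be compared"), so RR = 0.60, 0.65, 0.70 and 0.75. Alpha, power and incidence are not given. The absolute person-years therefore cannot be reproduced, and only the scaling can be tested.

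**1. Ratios between outcomes.**

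- Adults, VE 35/30/25/20%: ICU/hospitalization 6.07, 6.15, 6.14, 6.26; death/hospitalization 27.3, 27.0, 27.2, 27.1.
- Children, VE 40/35/30/25%: ICU/hospitalization 2.54, 2.46, 2.26, 2.15; death/hospitalization 70.5, 69.2, 62.7, 56.8.

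The adult ratios are constant within the rounding of the printed figures.

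**2. Growth relative to the 40% row, children.** Brackets give the range allowed by rounding.

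| Row | 35% | 30% | 25% |
|---|---|---|---|
| Hospitalization | 1.429 | 2.115 | 3.26 (3.14–3.39) |
| ICU | 1.39 | 1.88 (1.82–1.94) | 2.77 (2.71–2.84) |
| Death | 1.402 | 1.879 | 2.626 (2.62–2.63) |

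At 30% and 25% the ICU and death ranges do not reach the hospitalization values, so rounding is not the cause.

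**3. Could a different age mix by outcome explain it?** If one outcome fell mainly on younger children, effective coverage could lie anywhere from 50% to 70%. Take the log rate ratio formula with the overall rate fixed:

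PY ∝ [1/(1−c) + 1/(c·RR)] × (1−c + c·RR) / (ln RR)².

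- At c = 0.5 the growth from the 40% row is 1.985 (VE 30%) and 3.017 (VE 25%).
- At c = 0.7 it is 2.117 and 3.312.
- The spreads are 6.6% and 9.8%, the largest found in any formula tried.

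The observed gaps between hospitalization and death are 12.6% (2.115/1.879) and about 24% (3.26/2.626). For ICU they are about 12% and 18%. With rounding pushed as far as it goes towards agreement, the ICU gaps are still 9.0% and 10.7%. Age mix within one formula does not close them, although the ICU margin at 25% is then narrow.

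**4. The death row taken alone.** Each 5-point drop in VE should multiply person-years by more than the drop before it. With the log rate ratio, the unvaccinated rate fixed and c = 0.6, PY ∝ [1/(1−c) + 1/(c·RR)] / (ln RR)² gives steps of 1.35, 1.41, 1.49. I ran five formulas: log rate ratio, events-based (Schoenfeld), rate difference with pooled and with unpooled variance, and square root. Each was run with the unvaccinated, overall or vaccinated rate fixed, at coverage 50%, 60% and 70%. All gave rising steps.

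- Hospitalization row: 1.43, 1.48, 1.54, which rises.
- Death row: 1.40, 1.34, 1.40. With rounding the first step is 1.398–1.406 and the second 1.337–1.343, so the fall is real.

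**5. Size, under two anchors.**

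*Hospitalization row and 40% entries right.* Multiply each 40% entry by the hospitalization growth.

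- ICU: 1.01 × 2.115 = 2.14 m and 1.01 × 3.264 = 3.30 m, against 1.9 m and 2.8 m printed (11% and 15% low).
- Death: 28.1 × 2.115 = 59.4 m and 28.1 × 3.264 = 91.7 m, against 52.8 m and 73.8 m (11% and 20% low).
- Since 1.3 million may be anything from 1.25 to 1.35 million, the 25% shortfalls range over 12–18% (ICU) and 16–23% (death).

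*Hospitalization row and 25% entries right.* Divide each 25% entry by 3.264.

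- ICU: 2.8/3.264 = 0.858 m, so the printed 1.01 m is about 18% high.
- Death: 73.8/3.264 = 22.6 m, so the printed 28.1 m is about 24% high.

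**6. Detectable VE and power, first anchor only.** Interpolating on the hospitalization row, the printed 25% entries would detect a VE of about 27% (ICU) and 27.4–27.5% (death). For power, assume two-sided alpha 0.05 and use Φ((1.96 + z) × √share − 1.96), where z is the normal quantile of the intended power and share is 2.8/3.30 = 0.849 (ICU) or 73.8/91.7 = 0.805 (death). If 80% was intended, the result is about 73% (ICU) and 71% (death). If 90% was intended, it is about 85% and 83%.

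**The case against.** The strongest reply is that direction and cause are unknown and the consequence is small. Most of that stands.

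- **Direction.** A reader might infer that the pediatric ICU and death requirements are understated. The protocol does not support that. It depends on trusting the hospitalization row and the 40% entries; trusting the 25% entries reverses it. The ICU row alone lies close to an ordinary formula with the unvaccinated rate fixed at 60% coverage (1.90 and 2.82, against 1.88 and 2.77 printed).
- **Cause.** A reader might infer that ICU and death were computed with the unvaccinated rate fixed and hospitalization with the overall rate fixed. The death row fits neither convention: its best fit among the formulas tried misses by 4.5%.
- **Size.** A reader might take the 20% as an error in the minimum detectable VE. It is a person-year gap in one cell under one anchor.
- **ICU share.** The rows imply that 39–46% of hospitalized children enter ICU (1/2.54 to 1/2.15), against about 16% of adults. That looks odd, but the protocol gives no ICU share to set it against and the surveillance source is not at hand. It contradicts nothing.
- **Consequence.** The design is retrospective. Under section 5.1, sites contribute the seasons their records support, and no enrolment target hangs on Table 1. The row with the largest gap, death, is not an Objective 5 VE outcome.

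None of this reconciles the rows.

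**Conclusion.** The point holds as an internal contradiction in Table 1. Under the single set of assumptions in section 6.2, the pediatric hospitalization, ICU and death rows cannot all be right, and at least one death entry is wrong or rests on another basis. This relies on events being rare and on one method being meant for all outcomes, as the adult column suggests.

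Which row is wrong is open. The person-year discrepancy at the ends of the range is 15–18% for ICU and 20–24% for death, depending on the anchor. In detectable VE it is at most about 2.5 points under the first anchor. The power losses hold only under that anchor and the assumed alpha and power. The practical effect is modest and falls mainly on pediatric ICU admission.

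**What to change.** Recompute all pediatric rows of Table 1 with one formula, one convention for the baseline rate (unvaccinated or overall) and one incidence per outcome. Replace the figures that do not agree. Print the incidence for each outcome, alpha and power under the table so that it can be checked. Before reissuing, confirm that the ICU/hospitalization and death/hospitalization ratios are near constant down the pediatric column, as they are for adults.

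The cost is a recalculation and a table edit, with no new data and no design change. The revised figures may be higher or lower than those printed.
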